5.3 AEs coding/grading

Adverse events (AEs) are to be coded with the MedDRA dictionary based on the latest version available at the time of the analyses (version 25 or above) gives preferred term (PT) and primary system organ class (SOC) information.

5.4 Laboratory parameters derivations

[Table 5-1](#), [5-2](#), [5-3](#) and [5-4](#) show the criteria for clinically notable liver test values, renal function, skeletal muscle function and vital signs, respectively.

When a criterion contains multiple laboratory parameters, the criterion will only be considered to have been met when all conditions occur on the same assessment. A case where all criteria are met at a post-baseline time point will be considered as newly occurring if the criteria are not met at baseline and will be considered as worsening if the criteria are met at baseline and at least one component is worsening from baseline irrespective of whether the other(s) are better.

For additional safety monitoring see Section 10.2.2 and 10.2.3 of Protocol.

Table 5-1 Notable liver function test values

Criterion
ALT $\geq 3 \times$ the upper limit of normal range (ULN)
ALT $\geq 5 \times$ ULN
AST $\geq 3 \times$ ULN
AST $\geq 5 \times$ ULN
ALT or AST $\geq 3 \times$ ULN
ALT or AST $\geq 5 \times$ ULN
Total bilirubin $\geq 2 \times$ ULN
ALP $\geq 2 \times$ ULN
ALT or AST $\geq 3 \times$ ULN and total bilirubin $\geq 2 \times$ ULN
ALT = alanine aminotransferase, AST = aspartate aminotransferase, ALP = alkaline phosphatase

Table 5-2 Notable renal function

Criterion
eGFR ≥ 30 and ≤ 60 ml/min /1.73m ²
Moderate renal impairment
eGFR < 30 ml/min/1.73m ²
Severe renal impairment
eGFR = Estimated glomerular filtration rate

Table 5-3 Notable skeletal muscle values

Criterion
CK $> 5 \times$ the upper limit of normal range (ULN)
CK = Creatine kinase

Table 5-4 Notable Criteria for Vital Signs

Vital sign	Notable abnormalities
Pulse (bpm)	<40 or >180
BP (mmHg)	Systolic (SBP)
	<40 or >180 for Screening Visit
	<40 or >220 for Other Visits
	Diastolic (DBP)
	<40 or >110 for Screening Visit
	<30 or >130 for Other Visits

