5.1 Inclusion criteria

Participants eligible for inclusion in this study must meet **all** of the following criteria:

At Screening:

1. Written informed consent must be obtained before any assessment is performed.
2. Male or female participants ≥ 18 years of age.
3. Participants categorized as very high or high CV risk, as defined below:
 - **Very high risk participants** with at least one of the following:
 1. Documented ASCVD
 - ACS: Unstable angina or myocardial infarction
 - Stable angina
 - Coronary revascularization
 - Unequivocally documented ASCVD upon prior imaging
 - Stroke and Transient Ischaemic Attack (TIA)
 - PAD
 2. Diabetes mellitus (DM) with target organ damage (defined as microalbuminuria, retinopathy, or neuropathy), or at least ≥ 3 major risk factors, or early onset of Type 1 DM of long duration (> 20 years)
 3. A calculated SCORE2 $\geq 7.5\%$ for age < 50 years; SCORE2 $\geq 10\%$ for age 50-69 years; SCORE2-OP $\geq 15\%$ for age ≥ 70 years to estimate 10-year risk of fatal and non-fatal CVD

4. Pre-existing diagnosis of heterozygous familial hypercholesterolemia (HeFH) with ASCVD or with another major risk factor.

OR

- **High risk participants** with at least one of the following:
 1. Markedly elevated single risk factors, in particular total cholesterol > 310 mg/dL, LDL-C > 190 mg/dL, or blood pressure \geq 180/110 mmHg
 2. Pre-existing diagnosis of HeFH without other major risk factors
 3. DM without target organ damage (defined as microalbuminuria, retinopathy, or neuropathy), with DM duration \geq 10 years or other additional risk factor
 4. Moderate chronic kidney disease (eGFR 30-59 mL/min/1.73m²)
 5. A calculated SCORE2 2.5 to <7.5% for age under 50 years; SCORE2 5 to <10% for age 50-69 years; SCORE2-OP 7.5 to <15% for age \geq 70 years to estimate 10-year risk of fatal and non-fatal CVD

as defined by the cardiovascular risk categories in the 2019 ESC/EAS guideline ([Mach et al 2020](#)), [Note: Table 4, page 15: High risk and very high risk only] and updated SCORE2 and SCORE2-OP (according to [Hageman et al 2021](#), [de Vries et al 2021](#), [Visseren et al 2021](#)). Further details for documented ASCVD are provided in [Section 16.4](#).

4. LDL-C levels:
 - a. in participants with very high cardiovascular risk: serum LDL-C \geq 55 mg/dL.
 - b. in participants with high cardiovascular risk: serum LDL-C \geq 70 mg/dL

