
¹² Lp(a) will only be tested at screening, baseline, Day 90 and EOS. From this sample, triplicate serum aliquots will be made to allow Lp(a) testing in both nmol/L and mg/dL; a third aliquot will be made to allow testing of LDL-C and/or Lp(a) using novel methods currently in development.
 
¹³ A blood draw for PCSK9 levels will also be performed prior to participant switch to PCSK9 mAb, preferably once this switch is granted. The PCSK9 results will remain blinded and will not be used to influence treatment decisions. A plasma aliquot from the PCSK9 blood draw (e.g. SOMA) may also be used to profile proteins related to study drug or dyslipidemia.
 
¹⁴ AST, ALT, ALP, GGT, total bilirubin, CK, creatinine, creatinine clearance, eGFR, chloride, sodium, potassium, fasting glucose, HbA1C. Performed by the central lab.
 
¹⁵ ONLY: AST, ALT, ALP, GGT, CK, Total bilirubin. Performed by the central lab.
 
¹⁶ Hematocrit, Hemoglobin, Red Blood Cell (RBC) Count, Mean Corpuscular Volume (MCV), Mean Corpuscular Hemoglobin (MCH), Mean Corpuscular Hemoglobin Concentration (MCHC), Platelets, Erythrocyte Cell Morphology, White Blood Cell (WBC) count with Differential (Basophils, Eosinophils, Lymphocytes, Monocytes, Neutrophils, Bands). Performed by the central lab.
 
¹⁷ Urinalysis to include: specific gravity, pH, glucose, protein (total), ketones, bilirubin, urobilinogen, nitrite, hemoglobin (blood), leukocytes esterase. If dipstick measurement results are positive (abnormal), microscopic examination will be performed.
 
¹⁸ Done every day during the treatment period, using a digital hand-held device. Participant is to complete the diary everyday at home and the diary will be checked by the investigator at each site visit.
 
¹⁹ Training for each questionnaire should be completed with each participant prior to the first individual participant questionnaire completion.
 
²⁰ The Walking Impairment Questionnaire will only be completed by participants diagnosed with peripheral artery disease (PAD) at Baseline.
 
²¹ The Mac New Heart Disease Health Related Quality of Life Questionnaire will only be completed by participants diagnosed with Angina Pectoris (AP) at Baseline.
 
²² Theoretically, EOT and EOS happen on day 360, but if EOT occurs before the EOS visit, it is recommended that the participant remains in the study until the scheduled EOS. The assessments listed for this visit should only be conducted if the End of Treatment (EOT) and End of Study (EOS) occur simultaneously. An "early Exit" (premature discontinuation from study treatment and study on the same day before day 360) is considered as an EOS visit, and the assessments should be performed as they would be on EOS visit day 360. In case of premature treatment discontinuation, the assessments for the scheduled visit day should be performed (for details refer to Section 8.5.1 and Section 9.1.1).
																			

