2.1.1.5 Baseline

Baseline value is defined as the last non-missing value prior to the start of the treatment period, which means prior to the first injection of the blinded investigational treatment. If the date of assessment is the same as date of first injection but time is not available for comparison, the assessment is assumed to be prior to the administration of blinded investigational treatment. Questionnaires assessments at Day 1 are considered as baseline irrespective of time collected. Participants pain diary is not collected prior to first injection of the blinded investigational treatment, therefore baseline is not defined for the same.

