2.1.1.7 Visits

Measurements will be collected without windowing as defined in the protocol. Analysis windows will be used for analysis of the data as outlined in [Table 2-1](#).

Based on the study day a scheduled or unscheduled visit is performed, the visit will be allocated to the analysis visit within the corresponding analysis visit window. E.g., if the Day 30 visit of a participant is delayed and occurs on day 33 it will be allocated to analysis visit Day 30. In the case of deviations from the visit schedule, or due to unscheduled visits, several assessments of a participant may fall in a particular analysis window (either scheduled or unscheduled).

If two measurements are allocated to the same analysis window and one is scheduled and the other unscheduled, the scheduled visit will be prioritized regardless of the difference to the target day (even if the unscheduled visit is closer to target day). If at least two scheduled or at least two unscheduled visits are allocated to the same analysis window, the measurement closest to the target day/time will be used. In the event that two measurements are taken equally apart (e.g., one day before target date and one day after) and both are either scheduled or unscheduled the last one will be used.

In case an analysis visit for a specific assessment is not planned (e.g., vital signs at Day 60), the time span (in days) between two visits is split equally and mapped to the former or consecutive analysis visit window, respectively.

The mapped visits will be used in the 'by visit' analysis as allocated. However, the listings will contain all information regardless if the collected data is based on a mapped or not-mapped, scheduled or unscheduled visit.

Table 2-1 Analysis visit windows based on study days

Analysis window (study days)									
Analysis Visit	SF-BPI, GSRS, Clinical chemistry (if also in Limited Chemistry)	Clinical Chemistry (and not in Limited Chemistry)	Fasting lipid profile (includes LDL-C for efficacy analyses)	Hematology, Urinalysis	Fasting Lp(a)	PCSK9	Vital signs	SF-36	WIQ, Mac New, TSQM
Pre-dose	<= 1 pre-dose	<= 1 pre-dose	<= 1 pre-dose	<= 1 pre-dose	<= 1 pre-dose	<= 1 pre-dose	<= 1	<= 1	<= 1
Day 30	30 [1 post-dose, 45]	30 [2, 60]	.	.
Day 60	60 [46, 75]	.	60 [1 post-dose, 75]
Day 90	90 [76, 120]	90 [1 post-dose, 120]	90 [76, 120]	.	90 [1 post-dose, 225]	.	90 [61, 120]	90 [2, 150]	90 [2, 225]

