2.7.3 Laboratory data

Laboratory data consist of hematology, clinical/limited chemistry, lipid panel and urinalysis measurements.

Notable abnormal laboratory data will be listed by treatment group, participant, and visit/time and if ranges are available, abnormalities will be flagged. Shift tables based on the standard ranges for each laboratory parameter will be provided by treatment group at each visit to present incidence of transitions from a baseline high, normal or low laboratory value to a post-baseline high, normal or low value. Glucose should be measured fasting, non-fasting glucose values will be excluded from the analyses.

Number and percentages of participants with newly occurring or worsening notable liver-function, renal function and skeletal muscle laboratory values as defined in [Section 5.4](#) will be tabulated.

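### In the moderate renal row of SAP Table 5-2 any fall in eGFR, however small, counts as worsening, so most participants with baseline eGFR 30-60 could be flagged by measurement noise alone

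*SAP*

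**What the plan says.** SAP 2.7.3 plans a table of "Number and percentages of participants with newly occurring or worsening notable liver-function, renal function and skeletal muscle laboratory values" and refers to SAP 5.4 for the definitions.

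SAP 5.4 gives two routes into that table. The first covers participants who do not meet the criterion before treatment: "A case where all criteria are met at a post-baseline time point will be considered as newly occurring if the criteria are not met at" (the comparison is with the pre-treatment value). The second covers participants who already meet the criterion at baseline. Such a case "will be considered as worsening if the criteria are met at baseline and at least one component is worsening from baseline". Neither route sets a minimum size of change or asks for a repeat value.

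Table 5-2 has two renal criteria. The moderate one is "eGFR ≥ 30 and ≤ 60 ml/min" per 1.73 m². The severe one is eGFR below 30.

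Baseline is one value: "Baseline value is defined as the last non-missing value prior to the start of the treatment period" (SAP 2.1.1.5). In Protocol 5.1 one of the high-risk entry routes is "Moderate chronic kidney disease (eGFR 30-59" mL/min/1.73m²), so participants in the band are recruited by design. Exclusion criterion 12 in Protocol 5.2 removes eGFR below 30.

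**The concern.** The moderate criterion has a single component, so that component worsening means that eGFR is lower than at baseline. A participant with baseline 59 who once reads 58 is a case, on a fall of 1/59 = 1.7%. A change of category cannot be what is meant for this row, because a fall from the band to below 30 is newly occurring under the severe row.

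The upper bound also disagrees with the rest of the plan. Table 5-2 includes 60, while Protocol 5.1 and SAP 5.2 both give 30-59. A participant at 61 who once reads 60 becomes newly occurring moderate impairment.

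At stake is whether this row can inform the comparison of renal function. The protocol monitors renal function because of rosuvastatin (Protocol 10.2.2), and the protocol summary expects less intense background therapy in the inclisiran arm. If most participants in the band are flagged whatever happens, a real difference between arms would barely move the percentage.

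**Working it through.** **Inputs from the documents**
- Rule: lower than baseline and still in 30-60, at one post-baseline time point (SAP 5.4, Table 5-2).
- Baseline: one value (SAP 2.1.1.5).
- Follow-up values: eGFR is in full chemistry (Protocol Table 8-1, chemistry footnote: "creatinine, creatinine clearance, eGFR, chloride, sodium, potassium") and not in the limited panel. The SAP Table 2-1 column "Clinical Chemistry (and not in Limited Chemistry") has windows for Days 90, 150, 210, 270, 330 and 360, which makes six.

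The documents give no flag rate, so there is no figure to reproduce.

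**Assumptions, not in the documents**
- True eGFR is normal with mean 70, 75 or 80 and SD 18.
- Within-person CV is 4-10%, and eGFR is reported as an integer.
- There is no true change.

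**Step 1, closed form.** With independent noise and no selection, the baseline is equally likely to hold any rank among k + 1 values. The chance that at least one of k follow-up values is lower is 1 - 1/(k + 1) = k/(k + 1). For k = 1 this is 50%, for k = 3 it is 75%, and for k = 6 it is 6/7 = 85.7%. For this row 6/7 is a ceiling. Selecting on a baseline of 60 or below brings regression to the mean, the later value must stay in the band, and integer ties do not count.

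**Step 2, simulation of the rule as written**, in participants with baseline 30-60:

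| Reading | Flagged under no change |
|---|---|
| Any of six visits | about 70-76% |
| Per visit, averaged | about 33-38% |

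At mean 75, the any-visit rate is 70-73% with 10% of visits missing, and 70-72% with autocorrelated noise (correlation 0.5). Over a wider set of eGFR distributions (mean/SD 50/8 to 85/18, rounded or not) it runs from 67% to 85%. Day 360 read alone gives about 29-48% over that wider set.

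**Step 3, can the row show a signal?** Give 5% of one arm's participants in the band a sustained 30% fall. The any-visit worsening rate rises by only about 0.5-1.2 percentage points, for example from 75.0% to 75.8% at mean 75, CV 6%. If a fall of at least 25% within the band is required, the rate moves from 0.0-4.4% to 4.3-8.0%, a rise of 3.6-4.5 points.

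**Step 4, which change to the rule matters?** At mean 75, SD 18, under no change:

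| Rule | CV 5% | CV 8% | CV 10% |
|---|---|---|---|
| Fall of more than 10%, any visit | 18% | 35% | 41% |
| Fall of more than 20%, any visit | 0.2% | 5% | 10% |
| Fall of more than 25%, any visit | 0.01% | 1.1% | 3.6% |

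Over means 70-80 and CV 4-10%, a fall of at least 25% at any visit flags 0.0-5.1%. Asking for two consecutive visits with any fall still leaves 40-44%. The minimum change does most of the work.

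**Step 5, the severe row.** Under the Step 2 settings, 0.1-1.0% of all participants have any value below 30 when nothing has changed.

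**The case against.** The best defence is that the damage is confined to one row. Baseline eGFR below 30 is excluded, so apart from protocol deviations every severe case is newly occurring, and the any-fall rule cannot act there. SAP 2.7.3 also plans shift tables for each laboratory parameter at each visit and listings of notable values. SAP 2.7.1 plans adverse event summaries. All of this stands. A reader might infer that the plan has no usable renal output, and the documents do not support that. The shift tables do not, however, grade change within the low range, so they do not replace the moderate row.

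The second defence is that the three-quarters figure needs a count over any visit. SAP 2.7.3 does not say this for laboratory values, although SAP 2.7.4.1 says so for vital signs. This also stands, and it is why both readings are given. At 33-38% per visit the row is still mainly noise for this group, and the open wording is itself worth settling.

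Third, the rates rest on assumed eGFR distributions and variability. That is correct: they are a range, not a prediction.

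Fourth, the table carries no test and the noise is similar in both randomised arms. That is also correct. A reader might infer bias towards one arm, but nothing in the documents points that way.

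Fifth, requiring confirmation on two consecutive visits would be debatable. Full-chemistry visits are 60 days apart from Day 90 to Day 330, so transient falls would be lost, as would a fall first seen at Day 360. This is accepted: confirmation should not be the main rule.

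**Conclusion.** The point holds for the moderate row. The definition is complete enough to program as it stands, and it would give an uninformative percentage. With no true change, about 70-76% of participants with baseline eGFR 30-60 are flagged over any visit (ceiling 6/7 for independent noise), or about 33-38% per visit. This assumes mean eGFR 70-80, SD 18 and within-person CV 4-10%. That the rule sets no minimum change rests on the SAP text alone; the rates rest on the assumptions.

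The consequence is masking of a renal difference in a descriptive safety table. The confirmatory analyses are untouched. A reader might extend the result to a fixed share of the whole safety set, but that would depend on how many participants start in the band, and the documents do not give that number. The change is worth making before database lock because it is cheap.

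**What to change.** In SAP 5.4 and Table 5-2:

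1. For the moderate renal row, define worsening by a minimum decrease from baseline, for example at least 25% at any post-baseline assessment. The 25% is one workable choice and has no source in the documents. A version confirmed at two consecutive assessments can be added as an extra row.
2. State how a fall that leaves the band is counted. Since 0.75 × 40 = 30, a 25% fall from a baseline below 40 ends below 30 and enters the severe row. The no-change rate is about 0-5% whether or not the value must stay in the band.
3. Report newly occurring and worsening in separate rows.
4. State in SAP 2.7.3 that the count is over any post-baseline visit.
5. Set the upper bound of the moderate criterion to <60, to agree with the 30-59 range in Protocol 5.1 and SAP 5.2.

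The cost is SAP wording and one table program, with no new data. The downside is that smaller falls within the band leave the percentage. They can remain in the listing of notable values.

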- Recently approved bempedoic acid may also be considered for LLT escalation, however, it is not depicted in the current guidelines and should thus be used secondarily after the aforementioned substances. Please refer to [Figure 3-2](#).
- Then last, access to PCSK9 mAb as next escalation step will be handled according to the German prescribing restriction ([Bundesausschuss 2021](#)). The recommendation will be to use the latest version of the guidance and an English version will be made available.

PCSK9 mAb may be indicated in participants with a confirmed vascular disease (CHD, cerebrovascular disease, PAD) and regularly additional risk factors for cardiovascular events (e. g. diabetes mellitus, restricted renal function with $\text{eGFR} < 60 \text{ mL/min/1.73m}^2$), or in participants with a confirmed diagnosis of HeFH taking the overall family predisposition into account, if LDL-C cannot be reduced sufficiently despite in principle a documented maximum dietary as well as lipid-lowering drug therapy over a period of 12 months.

To ensure that a participant is allowed to receive the PCSK9 mAb therapy according to the referenced guidance, the Steering Committee (members of the PCSK9 mAb decision board), will review the required participant's data and decide on the participant's eligibility for such therapy ([Section 10.3.1](#)).

PCSK9 general decision:

In case a participant is deemed eligible, the participant will need to discontinue the blinded investigational treatment (inclisiran/placebo).

CCI [REDACTED] is the preferred PCSK9 mAb to be used to enable consistency in therapy among trial countries and will be supported by the sponsor. The participant will remain in the study despite having discontinued blinded investigational treatment (inclisiran/placebo) and will be followed-up until the participant's end of study.

- If the participant is deemed ineligible for switch to PCSK9 mAb by the Steering Committee, the Investigator is encouraged to continue the participant's LLT escalation as recommended in [Figure 3-2](#). If the investigator decides that a PCSK9-targeted therapy is indicated despite the decision of the SC, the participant will need to discontinue study treatment (inclisiran/placebo), and should be treated as per local standard of care and followed-up but should remain in the study until the participant end of study.

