6.6.3 Dose modifications

Blinded investigational treatment, inclisiran/placebo, dose adjustments and modifications are not permitted throughout the trial.

For open label study treatment, rosuvastatin, dose adjustments please refer to [Section 3.4](#) and [Section 10.2](#).

The 40 mg rosuvastatin dose is contraindicated in participants with pre-disposing factors for myopathy/rhabdomyolysis. Such factors include:

- moderate renal impairment (creatinine clearance < 60 mL/min)
- hypothyroidism
- personal or family of hereditary muscular disorders
- previous history of muscular toxicity with another HMG-CoA reductase inhibitor or fibrate
- alcohol abuse
- situations where an increase in plasma levels may occur
- Asian patients
- Concomitant use of fibrates.

In situations where co-administration of medicinal products causing an increase in systemic exposure of rosuvastatin or increased risk of myopathy is unavoidable, the maximum daily dose of rosuvastatin should be adjusted so that the expected rosuvastatin exposure would not likely exceed that of a 40 mg daily dose of rosuvastatin taken without interacting medicinal products (always refer to local rosuvastatin SmPC).

Generally, rosuvastatin should be prescribed with caution in participants with pre-disposing factors for myopathy/rhabdomyolysis.

Please note, specific types of genetic polymorphisms are known that can lead to an increased rosuvastatin exposure. For participants who are known to have such specific types of polymorphisms, a lower daily dose of rosuvastatin is recommended.

The initiation of treatment or dosage up-titration of rosuvastatin in participants treated concomitantly with vitamin K antagonists (e.g., warfarin or another coumarin anticoagulant) may result in an increase in International Normalized Ratio (INR). Discontinuation or down-titration of rosuvastatin may result in a decrease in INR.

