10.2.2 Renal safety monitoring

For the open label study treatment (rosuvastatin) renal function should be monitored and assessments are outlined in the Assessment Schedule (Table 8-1). Rosuvastatin is contraindicated:

- in participants with severe renal impairment (creatinine clearance <30 mL/min) regardless of the dose,
- in participants with moderate renal impairment (creatinine clearance <60 mL/min) with 40 mg dose rosuvastatin.

Proteinuria, detected by dipstick testing and mostly tubular in origin, has been observed in patients treated with higher doses of rosuvastatin, in particular 40 mg, where it was transient or intermittent in most cases. Proteinuria has not been shown to be predictive of acute or progressive renal disease.

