5.2 Stratification

The stratification factor is given by the CV risk group as defined in the following:

- Very high risk participants with at least one the following:
 1. Documented ASCVD
 - ACS: Unstable angina or myocardial infarction

- Stable angina
 - Coronary revascularization
 - Unequivocally documented ASCVD
 - Stroke and TIA
 - PAD
2. Diabetes mellitus (DM) with target organ damage (defined as microalbuminuria, retinopathy, or neuropathy), or at least ≥ 3 major risk factors, or early onset of Type 1 DM of long duration (< 20 years)
 3. A calculated SCORE $\geq 10\%$ for 10-year risk of fatal CVD
 4. Pre-existing diagnosis of heterozygous familial hypercholesterolemia (HeFH) with ASCVD or with another major risk factor.
- High risk participants with at least one of the following:
 1. Markedly elevated single risk factors, in particular triglycerides > 8 mmol/L (> 310 mg/dL), LDL-C > 4.9 mmol/L (> 190 mg/dL), or blood pressure $\geq 180/110$ mmHg
 2. Pre-existing diagnosis of HeFH without other major risk factors
 3. DM without target organ damage (defined as microalbuminuria, retinopathy, or neuropathy), with DM duration ≥ 10 years or other additional risk factor
 4. Moderate chronic kidney disease (eGFR 30-59 mL/min/1.73m²)
 5. A calculated SCORE $\geq 5\%$ and $< 10\%$ for 10-year risk of fatal CVD as defined by the cardiovascular risk categories in the 2019 ESC/EAS guideline ([Mach et al 2020](#)).

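### SAP Table 5-2 counts an eGFR of exactly 60 as moderate renal impairment, although every other renal cut-off in the SAP and protocol excludes 60

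*SAP*

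**What the plan says.** SAP 5.4 sets the criteria for clinically notable laboratory values. The first row of Table 5-2 is "eGFR ≥ 30 and ≤ 60 ml/min" per 1.73 m², labelled moderate renal impairment. The second row is eGFR below 30, labelled severe.

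SAP 5.4 also says how cases are classed. A post-baseline case "will be considered as newly occurring if the criteria are not met at baseline". It is worsening if the criterion was already met at baseline and the value has deteriorated. The same bound is therefore applied to the baseline value and to each later value.

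The output is described in SAP 2.7.3: "Number and percentages of participants with newly occurring or worsening notable liver-function, renal function and skeletal muscle laboratory values" are to be tabulated.

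The other renal limits read as follows:

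- SAP 5.2, high-risk criterion: "Moderate chronic kidney disease (eGFR 30-59 mL/min/1.73m²". Protocol 5.1 has the same range.
- Protocol 3.4, on access to PCSK9 antibodies: "restricted renal function with" an eGFR below 60.
- Protocol 6.6.3: "moderate renal impairment (creatinine clearance < 60 mL/min". Protocol 6.6.1.1 uses the same limit.
- Protocol 10.2.2, to which SAP 5.4 refers: "in participants with moderate renal impairment (creatinine clearance <60 mL/min) with 40 mg dose rosuvastatin".

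**The concern.** The value 60 lies inside the Table 5-2 category and outside every comparable category elsewhere. SAP section 4, which lists departures from the protocol's analyses, neither mentions nor explains it. The lower limit is consistent: 30 and above is moderate, below 30 is severe, and Protocol 5.2 excludes participants below 30. Only the upper limit is out of line, which looks more like a slip than a choice.

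The bound is an operative programming rule, and it acts in two ways. A participant who starts above 60 and whose only qualifying value is 60 becomes a newly occurring case. A participant who starts at 60 and later falls below it is treated as already notable at baseline, so the fall is recorded as worsening. What is at stake is the accuracy of one row in a safety table, in a trial whose arms are expected to differ in background lipid-lowering intensity.

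**Working it through.** **Step 1: compare the limits.** The plan states no count or power figure that depends on this bound, so there is nothing to reproduce. The first check is a direct comparison.

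| Place | Measure | Purpose | Is 60 included? |
|---|---|---|---|
| SAP 5.4, Table 5-2 | eGFR | Notable value, moderate renal impairment | Yes |
| SAP 5.2; Protocol 5.1 | eGFR | Moderate chronic kidney disease as a risk criterion | No (30-59) |
| Protocol 3.4 | eGFR | Restricted renal function | No (< 60) |
| Protocol 6.6.1.1, 6.6.3, 10.2.2 | Creatinine clearance | Moderate renal impairment, rosuvastatin use | No (< 60) |

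**Step 2: size the effect.** Inputs from the documents are 1,776 randomized participants (Protocol, Amendment 3 rationale) and six post-baseline full-chemistry visits, on Days 90, 150, 210, 270, 330 and 360 (Protocol Table 8-1). The eGFR comes from the MDRD formula (Protocol Table 8-3), with no reporting precision given.

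Assumed, not in the documents: normally distributed true eGFR with mean 70, 80 or 90 and between-person SD 15 or 20; within-person SD 4 or 7; no trend and no treatment effect. Simulated baselines below 30 were dropped, and counts were scaled to 1,776.

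Definitions:

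- New(≤ 60): baseline not in [30, 60], and at least one post-baseline value in [30, 60].
- New(< 60): the same with [30, 60).
- Added: new under ≤ 60 but not under < 60, that is, only through a value of 60.
- Shifted: new under < 60 but not under ≤ 60, that is, baseline exactly 60.
- Net = New(≤ 60) − New(< 60) = Added − Shifted.

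Selected results with eGFR rounded to integers, both arms pooled, including the extremes of all twelve settings:

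| Mean / SD / within-person SD | New(≤ 60) | New(< 60) | Added | Shifted | Net |
|---|---|---|---|---|---|
| 70 / 15 / 4 | 218.6 | 210.7 | 37.6 | 29.6 | 7.9 |
| 70 / 15 / 7 | 382.9 | 373.4 | 38.3 | 28.8 | 9.5 |
| 70 / 20 / 7 | 305.4 | 300.9 | 29.0 | 24.5 | 4.5 |
| 80 / 15 / 4 | 129.1 | 118.2 | 25.0 | 14.1 | 10.9 |
| 80 / 15 / 7 | 248.1 | 233.5 | 29.1 | 14.4 | 14.7 |
| 90 / 15 / 4 | 49.5 | 43.7 | 10.8 | 5.0 | 5.8 |
| 90 / 20 / 4 | 74.8 | 70.5 | 13.8 | 9.5 | 4.3 |

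Small differences in the last digit are rounding. Over the twelve settings the net change is 4.3 to 14.7 participants. As a share of New(≤ 60) it runs from 4.5 / 305.4 = 1.5% to 5.8 / 49.5 = 11.7%. Added runs from 11 to 38 and Shifted from 5 to 30.

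A run with proportional within-person variation (CV 6% or 9%, mean 70 to 80, SD 18, integers) gave newly occurring rates of 9.17% vs 8.65%, 7.30% vs 6.78%, 10.78% vs 10.34% and 14.87% vs 14.15%. The differences are 0.44 to 0.72 percentage points. On 1,776 that is 0.0044 × 1,776 = 7.8 to 0.0072 × 1,776 = 12.8 participants, inside the range above.

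**Step 3: repeat without rounding.** With unrounded eGFR every setting gave Added = Shifted = Net = 0, because a continuous value is almost never exactly 60. With one decimal, the reported value 60.0 covers an interval one tenth as wide as the integer 60, so the effect is about a tenth of that in Step 2.

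**Step 4: layout of the table.** SAP 2.7.3 does not say whether newly occurring and worsening cases get separate rows. If they form one count, the Shifted participants appear under either bound. The offset then disappears and the difference is the Added figure, 11 to 38 with integers.

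**The case against.** The best case for leaving the row alone is that the documents contain no single definition to breach. The 30-59 range defines moderate chronic kidney disease as a cardiovascular risk criterion. The protocol's moderate renal impairment is stated in creatinine clearance, a different measure. Table 5-2 is the only place that attaches that label to an eGFR range. An inclusive bound may also be a flagging convention: Table 5-1 uses ≥ 3 × ULN for transaminases and ≥ 2 × ULN for bilirubin, where Protocol 10.2.1 uses strict inequalities for its combined criterion.

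The first part stands as a limit on the wording. A reader might infer that some new cases are not impairment by the trial's definition, but the documents give several related cut-offs, not one definition. What remains is that none of them includes 60. The convention argument is weaker, because Table 5-3 uses a strict bound (CK > 5 × ULN) and the SAP states no such convention.

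Four stronger readings are tempting and not supported:

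- *True cases are lost.* They are relabelled. A fall from 60 to below 60 still appears as worsening in the planned tabulation.
- *The comparison between arms is diluted.* The simulations assume no treatment effect, so they cannot show this, and the same rule applies to both arms.
- *This is the only view of renal change.* SAP 2.7.3 also plans laboratory shift tables on standard ranges, and SAP 2.7.1 tabulates adverse events by system organ class and preferred term.
- *The counts will clash with a reported eGFR 30-59 group.* No such group is planned. SAP 2.2.1 and 2.3.2 report risk only as high or very high.

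**Conclusion.** The inconsistency is confirmed by direct reading, and SAP section 4 does not declare it. Its practical effect is small and conditional. With integer eGFR, the newly occurring count changes by a net 4 to 15 of 1,776 participants over both arms. With unrounded values the change is practically zero. These figures rest on assumed eGFR distributions and show only the order of magnitude; the safety set may also be slightly smaller than 1,776. The table is descriptive, so no hypothesis test, alpha allocation, endpoint, stratum or eligibility decision is touched. It is a minor point, worth correcting because the correction is nearly free.

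**What to change.** Change the first row of Table 5-2 to eGFR ≥ 30 and < 60 mL/min/1.73 m², and apply it to both the baseline and the post-baseline classification. It would help to state the reporting precision of eGFR as well, since < 60 and 30-59 coincide exactly only for whole numbers. If including 60 was intended, SAP section 5.4 should say so and give the reason. The cost is one character in the table and one line of derivation code. No additional data are needed.
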